## 7.6.4 Views of men and women who declined participation or were consented and then either did not engage with the intervention or dropped out of the study

We will seek the views of eligible men and women who at some stage in the recruitment process decide to decline participation and the views of participants who withdrew or did not attend the intervention. It is likely that participants who drop out of the study will be less willing to talk to the researchers but we would try to capture their views where they are willing to give consent to a final 'exit' interview. Possible questions would include reasons for dropping out and whether continuing participation (and engagement in the intervention) could be supported. Whereas we would seek the views of decliners during the recruitment process with some gentle, impromptu and informal follow up questions, participants who drop out of the intervention or from the study will be conducted by telephone. The brief questions will last less than 10 minutes unless the participant wants to give more significant feedback. We would attempt to contact the participants who drop out of the study up to three times.

# 7.6.5 Views of men who are excluded from the study because they do not fulfil inclusion criteria

As a separate sub-study, outside the context of the pilot trial, we plan to seek consent for indepth semi structured interviews with a purposive sample of men not eligible for the study due to reasons such as sexual preference (i.e. no women partners or ex-partners), unstable drug or alcohol abuse, insufficient command of English or mental health issues which prohibit engagement in the study. The reason for doing these interviews is to make sure that we have some understanding of how the intervention might be adapted for more marginalised groups. Participants will be selected using maximum variation and interviews will focus on the criteria used for exclusion and possible ways to be more inclusive. It is anticipated that the interviews would last between 30 minutes and 1 hour and would be conducted either face-to-face (with an interpreter present if necessary) or carried out by phone.

We will use a safety protocol for all face-to-face interviews and a lone worker checking-in system (see Safety protocol appendix 1). As far as possible, a neutral, safe location will be used for interviews, with a responsible person nearby. (See Safety protocol, appendix 1)

## 7.6.6 Experience of intervention providers

Semi structured interviews will be carried out with all the intervention group facilitators, risk assessors (if different from facilitators), facilitators' supervisory managers, women's advocates and associated staff if appropriate. These interviews will be carried out at the end of the intervention and focus on the acceptability, strengths and weaknesses of the intervention, how the intervention compares with other interventions experienced, views on the suitability criteria and perceived effectiveness of programme. It is anticipated that the interviews would last approximately hour and would be conducted either face-to-face or by phone. Shorter telephone interviews will also be conducted at an earlier stage with a sample of professionals referring men into the pilot trial. These interviews will be conducted during the recruitment period to help ensure that any difficulties or obstacles to recruitment that we have the opportunity to address issues highlighted. Possible questions might include: the demographic and mental health profiles of men they work with; the perceived success of recruitment methods; who they think the intervention was most suitable for; and the referral process.

## 7.6.7 Observation of process

Observations from the facilitator training sessions, intervention group videos and ongoing weekly feedback from facilitators will be collected. These observations and weekly feedback will help inform the intervention provider interviews and provide data for understanding study retention (intervention arm) and fidelity to the programme manual. Researchers will also systematically note observations outside of the intervention, such as comments by participants when completing questionnaires. Observation guides will be developed and shared within the team to support the researchers in this recording process.

The sampling matrix below gives an idea of numbers of interviews planned but these may change depending on whether we feel adequate information is captured at an earlier stage or needs slightly more exploration (data saturation).

Participants	Intervention	Control	
Male perpetrators	15	5	
Female partners and ex partners	5	5	
Excluded participants	Up to 10		
Participants who withdraw or drop out	We will informally seek the views of all participants who withdraw or drop out where possible.		
Staff associated with intervention	Up to 10		

#### Sampling matrix

#### 7.7 Withdrawal criteria

- A participant will be withdrawn from the intervention trial if it becomes known that
  participation leads to an increase in danger to their partner or ex-partner or their
  children or the intervention facilitators. Similarly, if the danger extends to the
  research team, they will be withdrawn from the study. These decisions will be taken
  by the CI and programme manager in consultation with the DMEC and in
  collaboration with the DVPP facilitators. These decisions will be documented
  appropriately.
- The follow up of participants that have withdrawn from the intervention will continue so long as the participant still consents to be included.

## 7.8 End of trial

As this is a pilot trial, we will determine whether to progress to the full trial based on prespecified criteria:

Criteria to move to full trial	Determined by
Recruitment of participants	Rate and source of recruitment and sufficient number in order to meet progression criteria
Retention of participants	Up to 9 months post randomisation in order to meet progression criteria

Criteria for progression to full trial:

- The recruitment of 36 men within 9 months and/or a steady state recruitment rate that is consistent with this aim.
- follow up of male participants of 0.6 (95% ci 0.4 to 0.8) at 1 year
- follow up of female participants of 0.5 (95% ci 0.4 to 0.7) at 1 year

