## TRIAL SUMMARY

Trial Title	Feasibility of a randomised controlled trial of a group programme for men who are concerned about their behaviour in relationships with women: pilot study		
Internal ref. no. (or short title)		Group programme for men who are concerned about their behaviour in relationships with women: a pilot trial	
Phase	pilot trial		
Trial Design	Individual randomisation		
Trial Participants	Men aged 21 and over and th partners (aged 18 or over)	Men aged 21 and over and their female partners or expartners (aged 18 or over)	
Planned Sample Size	36 men plus their current or e sample size of up to72)	36 men plus their current or ex-partners (a total planned sample size of up to72)	
Treatment duration	The intervention programme i	The intervention programme is for 26 weeks	
Follow up duration	Up to 9 months	Up to 9 months	
Planned Trial Period	March 2017 – September 201	March 2017 – September 2018	
	Objectives	Outcome Measures	
Primary	Sufficient men and partners recruited in order to meet progression criteria	Number of participants	
Secondary	Sufficient men and partners retained and followed up in order to meet progression criteria	Number of participants	

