#### 3. OBJECTIVES AND OUTCOME MEASURES/ENDPOINTS

#### Objectives:

(i) To recruit and randomise 36 male perpetrators. *Two thirds* of the men (24) will be randomised to a community-based perpetrator programme and **one third (12)** to the control normal care group.

(ii) To recruit female partners / ex-partners of the men who have been accepted onto the study.

(iii) To measure recruitment rate, adherence of participants, fidelity of intervention and retention, and improvement in safety or feelings of safety for partners and ex-partners(iv) Identification of main cost drivers;

(v) To determine the acceptability of the intervention to perpetrators, and to their partners and ex-partners, the willingness for all participants to be randomised, the suitability of the primary outcome measure and the motivation for participation.

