## 9 STATISTICS AND DATA ANALYSIS

For the purposes of this pilot trial, data will be analysed and reported using descriptive statistics only as the pilot is not sufficiently powered for a comparison of outcomes between the groups. However, the findings from this pilot will inform the power calculation required for the full trial and a Statistical Analysis Plan will be produced once the findings from this pilot are reviewed and it is clear that progression to a full trial will happen. The SAP will be developed once the full trial primary and secondary outcomes are determined. Data on recruitment, randomisation and retention will be collected and recorded in line with CONSORT guidelines. All secondary outcome measures will be analysed and presented by trial arm for the baseline and 9 month time point to inform trial primary objectives.

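### Section 7.8: the women's follow-up criterion of 0.5 and its 95% interval of 0.4 to 0.7 do not agree if 0.5 is exact, so it is unclear whether 18 of 36 women would meet it

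*Protocol*

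**What the plan says.** Section 7.8 of the protocol (End of trial) lists three criteria for progression: recruitment of the men, follow-up of the men and follow-up of the women. The women's criterion reads "follow up of female participants of 0.5 (95% ci 0.4 to 0.7) at 1 year". The men's reads "follow up of male participants of 0.6 (95% ci 0.4 to 0.8) at 1 year".

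The section gives no denominator and no interval method. It does not say whether the observed proportion or a confidence limit is compared with the criterion.

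The denominators have to be taken from elsewhere. The trial summary gives "36 men plus their current or ex-partners (a total planned sample size of up to72"), which leaves at most 72 − 36 = 36 women. The objectives in section 3 give a number for the men ("To recruit and randomise 36 male perpetrators") but none for the women ("To recruit female partners / ex-partners of the men who have been accepted onto the study"). Section 9 says that "data will be analysed and reported using descriptive statistics only as the pilot is not sufficiently powered for a comparison of outcomes between the groups".

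**The concern.** At an observed proportion of exactly one half, every standard binomial interval is symmetric about 0.5. Limits of 0.4 and 0.7 lie 0.1 below and 0.2 above it. The men's line beside it can be reproduced from the planned number of men, so the women's line stands out.

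The figure sits in a go/no-go rule. Section 7.3 adds that the recruitment and retention of women will inform whether abuse reported by men, by women or by both becomes the primary outcome of the full trial. If the point value and the interval come from different counts, the group judging progression cannot tell which count was intended as the bar.

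**Working it through.** **Inputs.** Proportions and limits, to one decimal: section 7.8. Men: 36 (section 3). Women: at most 36 (trial summary). Confidence level 95%, taken as two-sided, z = 1.96. The method is not stated, so Wald, Wilson and exact (Clopper-Pearson) limits are shown. Wald: p ± 1.96·√(p(1−p)/n).

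**1. The men's figure, p = 0.6, n = 36.**
- Wald: √(0.6·0.4/36) = 0.0816; 1.96 × 0.0816 = 0.160; limits 0.440 to 0.760.
- Exact: 0.424 to 0.759.
- Both print as 0.4 to 0.8, as in the protocol. Wilson gives 0.438 to 0.743, which would print as 0.4 to 0.7.

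**2. The women's figure, p = 0.5 exactly, n = 36 (18/36).**
- Wald: √(0.5·0.5/36) = 0.0833; 1.96 × 0.0833 = 0.163; limits 0.337 to 0.663.
- Wilson: 0.345 to 0.655 (lower limit 0.3447 before rounding).
- Exact: 0.329 to 0.671.
- All three print as 0.3 to 0.7.

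**3. Could another n rescue an exact 0.5?** By symmetry the limits are L and 1 − L. For the lower limit to print as 0.4, L must be at least 0.35. The upper limit is then at most 0.65 and prints as 0.6, apart from an exact tie. For Wald, L = 0.35 needs n = 1.96² × 0.25 / 0.15² = 42.7, so 43 women, which is above the maximum of 36. A search over n from 2 to 399 with seven methods found no n that prints 0.4 to 0.7 at exactly 0.5.

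**4. If 0.5 is itself a rounded value.** 19/36 = 0.528 prints as 0.5.

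| Method | Limits for 19/36 | Printed to one decimal |
|---|---|---|
| Wald | 0.365 to 0.691 | 0.4 to 0.7 |
| Wilson | 0.370 to 0.680 | 0.4 to 0.7 |
| Exact | 0.355 to 0.696 | 0.4 to 0.7 |

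The exact lower limit is 0.3549 before rounding, so to two decimals it is 0.35. Other counts, such as 18/33 and 19/35, also print as 0.5 (0.4 to 0.7).

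**5. Size of the mismatch with 36 women.** The printed width is 0.7 − 0.4 = 0.30. At 18/36 the width is 0.310 (Wilson), 0.327 (Wald) or 0.342 (exact).

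**6. If fewer women enrol.** The protocol gives no expected number, so these sizes are assumed for illustration only. Exact interval at 0.5: 0.29 to 0.71 with 24 women; 0.26 to 0.74 with 18.

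**The case against.** The strongest reply is that nothing is wrong beyond one-decimal printing. A count of 19 of 36 gives the printed line by every method tried. The men's 0.6 × 36 = 21.6 is not a whole number either, so a rounded count may lie behind that line too. This stands as a possible reading, and it rules out saying that the interval fits no number of women the trial can enrol.

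It does not clear the text:
- The men's line supports it under some methods only. With 22/36, the exact (0.435 to 0.769) and Wilson (0.449 to 0.752) limits print as 0.4 to 0.8. Wald gives 0.452 to 0.770 for 22/36, printing 0.5 to 0.8, and 0.422 to 0.744 for 21/36, printing 0.4 to 0.7. Under Wald the men's line needs 0.6 itself, while the women's line needs a rounded value.
- It needs a fairly high number of women. The smallest n that prints the women's line is 31 by the exact method, 28 by Wald and 24 by Wilson.
- If 19/36 was meant, 0.5 is not the intended threshold: 18/36 would pass as printed and fail as intended.

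Three stronger readings are tempting, and the documents do not support them.
- A reader might infer that the women's interval claims more precision than the men's, because it prints as 0.3 wide against 0.4. That is a rounding artefact: with 36 in each group the Wald widths are 0.327 and 0.320.
- A reader might infer that the lower limit of 0.4 wrongly rejects results compatible with 0.5. Section 7.8 does not make the lower limit the deciding quantity. The printed 0.4 may stand for anything from 0.35 upwards, so probabilities computed against exactly 0.4 would mislead.
- A reader might infer that the trial expects far fewer than 36 women. The protocol gives only a maximum.

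**Conclusion.** The point holds in a limited form. Read as a target of exactly 0.5, the women's criterion does not agree with its own interval, which at 36 women is 0.33 to 0.67 by the exact method. Read as a rounded proportion, the interval is right but the threshold is higher than the figure shown. The protocol does not say which applies, so whether 18 of 36 meets the criterion is open.

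The numerical effect is small. With all 36 women, the stated width is 0.01 to 0.04 too narrow and the threshold is uncertain by one woman. The precision gap would matter more only with clearly fewer women, and that rests on assumed numbers. No sample size or analysis depends on it. It deserves correction because it is one of three progression criteria and the correction is cheap.

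The conclusion assumes a two-sided 95% binomial interval, conventional rounding and a maximum of 36 women.

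**What to change.** Restate the women's line in section 7.8 with count, denominator and a two-decimal interval, naming the method. Use one of:
- 18 of 36 women, 0.50 (exact 95% CI 0.33 to 0.67), if the target is one half;
- 19 of 36 women, 0.53 (exact 95% CI 0.35 to 0.70), if that count lies behind the printed limits.

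Say that 36 is the maximum denominator and that the interval widens if fewer women join. Add a clause saying whether the observed proportion is what is compared with the criterion.

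The cost is one line of text. The first version makes the stated precision slightly less favourable; the second makes explicit a bar one woman higher.

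Separately, the same line refers to one year, while the table above it in section 7.8 gives retention as "Up to 9 months post randomisation in order to meet progression criteria". The point made here does not depend on that difference, but the two should be reconciled in the same edit.

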## 8 Safety reporting

For this trial of a complex intervention, we will use the definitions assigned by Good Clinical Practice and more commonly used in trials of medication. We acknowledge that the risks in this population for AEs and SAEs is high, so will have protocols in place for recording and appropriately reporting.

## 8.1 Definitions

Term	Definition
Adverse Event (AE)	Any untoward medical occurrence in a participant in the trial, including occurrences which are not necessarily caused by or related to being part of the trial.
Serious Adverse Event (SAE)	
 
A serious adverse event is any untoward medical occurrence that:
 
results in death
 
is life-threatening
 
requires inpatient hospitalisation or prolongation of existing hospitalisation
 
results in persistent or significant disability/incapacity
 
consists of a congenital anomaly or birth defect
 

	Other 'important medical events' may also be considered serious if they jeopardise the participant or require an intervention to prevent one of the above consequences.
	NOTE: The term "life-threatening" in the definition of "serious" refers to an event in which the participant was at risk of death at the time of the event; it does not refer to an event which hypothetically might have caused death if it were more severe.

Protocol version 2.0 09/02/2018\_track changes

Please refer to the safety and ethical conduct SOP in appendix 1.

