## 3.3 Exploratory endpoints/outcomes

Objectives	Outcome Measures	Timepoint(s) of evaluation of this outcome measure (if applicable)
Trial: To assess recruitment and randomisation rate of men and their (ex) partners.	Number recruited and randomised in pilot trial	During 9 months
Trial: To assess retention of men and their (ex) partners.	Number retained during follow- up period.	During 9 months
Trial: To assess questionnaire completion	Completed data sets from PHQ-9, GAD-7, PTSD, EDQ5 and SF12 scale. Impact Toolkit questionnaire completion.	3, 6 and 9 months post randomisation.
	ICECAP-A capability measure	At 9 months post randomisation only
Trial: To develop fidelity framework for intervention	A method to assess fidelity in the main trial	During 12 months

Trial: Identify and pilot the collection resource use data and the associated unit costs	Best method for collecting data on use of health and social care services and other related costs associated with the trial.	During 12 months
Intervention: To determine the acceptability of the intervention to perpetrators, associated victims/survivors and staff.	Qualitative interviews	Time points throughout the 18 month pilot trial.
Trial: Assess the willingness and risks faced by female partners and ex-partners to be involved in the pilot trial	Impact toolkit questionnaire; qualitative interviews; collection of adverse incidents/adverse events/serious adverse events	Time points throughout the 18 month pilot trial.
Trial: Explore ways of improving retention in both the intervention and control arms for male and female participants	Engagement with PPI groups; qualitative interviews	Time points throughout the 18 month pilot trial.
Intervention Assess the mechanisms of support and supervision needed for those involved in the delivery of the intervention	Qualitative interviews and feedback sessions.	Time points throughout the 18 month pilot trial

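### AE and SAE definitions cover only medical occurrences in participants, so non-medical abuse of partners and any harm to children or non-participants have no defined reporting route

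*Protocol*

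**What the plan says.** Section 8 states that "we will use the definitions assigned by Good Clinical Practice and more commonly used in trials of medication". Section 8.1 then defines two categories. An AE is "Any untoward medical occurrence in a participant in the trial", whether or not related to the trial. For the other, "A serious adverse event is any untoward medical occurrence that" meets one of the usual criteria (death, threat to life, hospital admission and so on). A further clause on other important events is also confined to medical events.

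Elsewhere the protocol describes harm differently. Section 7.7 withdraws a man if it becomes known that "participation leads to an increase in danger to their partner or ex-partner", and extends this to children and facilitators. Secondary objective 5 (section 3.2) concerns the risks that female partners and ex-partners face. For that objective, section 3.3 lists the Impact toolkit, qualitative interviews and "collection of adverse incidents/adverse events/serious adverse events".

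Section 8.2 sends SAEs to the PI and DMEC chair within 48 hours. Appendix 5 sends SAE and AE forms to the Programme Manager and has the PSC/DMEC review both categories.

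**The concern.** The definitions come from drug trials, where harm is medical and falls on the person treated. Here the man receives the programme and much of the foreseeable harm falls on someone else, often in a form that is not medical. The Background section's own description of domestic violence and abuse includes controlling, coercive and threatening behaviour.

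Under 8.1 as written, a man in the programme whose abuse escalates without a health consequence for an enrolled woman generates no AE or SAE. The DMEC advises on whether to continue, modify or stop. The progression criteria in section 7.8 cover only recruitment and follow-up, so committee review is the main safety check before a full trial. A summary of AEs and SAEs alone could look reassuring while the kind of event described in 7.7 was taking place.

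**Working it through.** No significance level, power or effect size is involved. The check sets the sections side by side.

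**Who is a participant.** The Trial Summary plans "36 men plus their current or ex-partners (a total planned sample size of up to72", so at most 72 − 36 = 36 women. Children, facilitators, and partners who decline, are excluded or cannot be reached are not participants.

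**Applying 8.1 to typical events.**

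| Event | Medical? | In a participant? | AE/SAE under 8.1? |
|---|---|---|---|
| Assault injuring an enrolled woman, no hospital care | yes | yes | AE |
| Assault on an enrolled woman leading to admission | yes | yes | SAE |
| Abuse that worsens an enrolled woman's mental health | yes | yes | AE |
| Threats or coercive control of an enrolled woman, no health effect | no | yes | no |
| Police call-out or safeguarding referral, no injury | no | yes | no |
| Injury to a partner who declined | yes | no | no |
| Injury to a child or facilitator | yes | no | no |

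**Comparing with the harm the protocol names.** Section 7.7 covers danger of any kind to partner, children and facilitators, enrolled or not. Section 7.2 has declining women told of the man's allocation because it may bear on their safety and their children's. The last four rows fall within what those sections worry about and outside 8.1.

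**Counting categories.** Section 3.3 names three: adverse incidents, AEs and SAEs. Section 8.1 defines two. Section 8.2 and Appendix 5 between them route the same two. Adverse incidents have no definition, form or route in the text shown.

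**Other ways the events might surface.**
- 7.7: the DMEC is consulted on withdrawals for danger. This is case by case, once the danger is known.
- 8.2 and 8.3: the TSC/DMEC reviews safety information in general every six months, and the DMEC looks for trends in the safety data as a whole. Neither term is defined.
- 8.2: a safeguarding procedure applies to a child or adult at significant risk. No link back to the safety record is stated.
- Table 1: the women's Impact questionnaire is given at baseline, 3, 6 and 9 months, to enrolled women only. The progression target for female follow-up is 0.5.
- 7.6.3 and the sampling matrix: interviews with 5 women per arm.
- 7.3.13: police offender reports appear as a heading only.

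**Size.** The number of partners outside the AE definition is 36 minus the number who join, so anywhere from 0 to 36. The protocol gives no expected rate. Assuming 30% to 60% do not join: 36 × 0.30 = 10.8 and 36 × 0.60 = 21.6, or about 11 to 22 women. This counts people whose harm could not be an AE, not events.

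**The case against.** Four stronger readings are tempting, and the documents support none of them.

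- A reader might infer that this harm never reaches the DMEC. Section 7.7 consults the DMEC on exactly this danger, and the reviews in 8.2 and 8.3 are not worded as AE/SAE only. What remains is that review depends on an event having been recorded, and nothing shown requires that.
- A reader might infer that all abuse of partners is outside AE reporting. Consenting women are participants, and an AE needs no hospital care, so an assault that injures one is covered.
- A reader might infer that secondary objective 5 would be answered as if no harm had occurred. It also draws on the Impact toolkit and interviews, and abuse is a measured outcome in both arms.
- A reader might infer that no procedure exists for these events. Section 8.1 refers to an Appendix 1 safety SOP and 8.2 to an Appendix 2 safeguarding flowchart. Neither is in the text available, and either may add procedures. The absence of a definition or route can be asserted only for the text shown.

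Two objections bear on the remedy, and both stand. Recording events about people who never consented needs limits. By-arm counts would also be distorted. Intervention men have up to 26 weekly contacts and their partners a dedicated worker; control men complete questionnaires only, and control women are signposted or given a generic worker. More incidents would come to light in the intervention arm even if true rates were equal.

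It can also be said that this is a small descriptive pilot with openly declared GCP definitions. That limits the consequence but does not reconcile section 8.1 with 3.3 and 7.7.

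**Conclusion.** The concern holds as a mismatch of definitions. Sections 8 and 8.1 confine AEs and SAEs to medical occurrences in participants. Non-medical abuse of an enrolled woman, and any harm to children, facilitators or non-participating partners, is therefore outside the defined AE/SAE route, although 7.7 treats that danger as grounds for withdrawal and 3.3 counts on adverse incidents to measure women's risk. Other routes may bring such events to the DMEC; the text shown does not ensure that they are systematically recorded and do so.

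The conclusion rests on the wording alone. The range of 11 to 22 women illustrates the assumed 30% to 60% non-participation, and the point does not depend on it. The unseen Appendix 1 and 2 material could narrow the gap; if it does, 8.1 should say so. The wording should be settled before safety conclusions are drawn from the pilot.

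**What to change.** Reconcile sections 3.3, 7.7, 8.1 to 8.3 and Appendix 5 by defining in 8.1 the adverse incident category that 3.3 already names.

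- **Content:** new or escalated abuse or threats; police call-out or arrest for domestic violence and abuse; safeguarding referral; any event considered under 7.7.
- **Whose events:** participants. Also children, staff and non-participating partners, in de-identified form and only when the event becomes known through existing trial or safeguarding contacts.
- **Route:** the existing AE form and the existing Programme Manager/CI/DMEC pathway, with a cross-reference to the Appendix 1 SOP.
- **Reporting:** descriptive counts by arm, with the numbers randomised (24 and 12 as planned) and the source of each report. State that closer contact in the intervention arm makes detection unequal.

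No treatment or withdrawal rule changes. The cost is protocol and form wording, more events to log and review, and by-arm counts that cannot be read as comparative rates.
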